1.2. OUTCOME RESEARCH QUESTIONS

For each outcome research question listed above, whether a descriptive or impact design, summarize the inputs (e.g., program components, program supports, implementation features, etc.), target population (e.g., the population for which the effect will be estimated) and the outcomes (e.g., child well-being, father-child engagement, etc.) that will be examined to answer the research question(s). Comparisons for descriptive evaluations may reflect circumstances before the grant, pre-treatment, or pre-determined benchmark from other studies with similar interventions.

Research Question Number Should correspond to the number indicated in Table 1.1 above	Intervention Program component or set of activities that the evaluation will test or examine	Target Population Population for which the effect of the treatment will be estimated	Comparison What the intervention will be compared to (e.g., pre-intervention for descriptive designs)	Outcome Changes that are expected to occur as a result of the intervention	Confirmatory or Exploratory? Confirmatory: those upon which conclusions will be drawn Exploratory: those that may provide additional suggestive evidence
R1	Primary curricula (Next Level Fatherhood); Support Services (Case Management, Life Coaching);	Urban fathers who are 18+ years with children up to 24 years	Assessment of healthy parenting behavior at GWA Project enrollment.	Participants who complete primary and support services will report healthier parenting behavior	Confirmatory

	Continuous Quality Improvement (CQI) Process			one year after GWA Project enrollment.	
R2	Primary curricula (Next Level Fatherhood); Support Services (Case Management, Life Coaching); Continuous Quality Improvement (CQI) Process	Urban fathers who are 18+ years with children up to 24 years	Assessment of healthy parenting attitudes at GWA Project enrollment.	Participants who complete primary and support services will report healthier parenting attitudes one year after GWA Project enrollment.	Confirmatory

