8. DATA COLLECTION

8.1. CONSTRUCTS AND MEASURES

Clearly articulate the constructs of interest, measures to evaluate those constructs, and specific data collection instruments. Provide any information on the reliability and validity of the data collection instruments. For standardized instruments, you may provide the citation for the instrument.

Construct	Measure	Instrument	Reliability and Validity (if standardized instrument, you provide a citation for the instrument)
Parenting Attitudes	7 items: frequency of key attitudes (categories, 5-point scale)	nFORM Community-Based Fathers Survey (A3: a-g)	nFORM
Parenting Behavior	1 item: hours spent w/ children in last 30 days (interval); 1 item: frequency reach out to children (categories, 5 point scale); 7 items: frequency engage in key behaviors (categories, 5-point scale)	nFORM Community-Based Fathers Survey (A2b, A2c, A5b: b-d, f-i)	nFORM
Co-Parenting Behavior	11 items: frequency of agreement with key co-parenting behaviors (interval, 5-point scale)	nFORM Community-Based Fathers Survey (A13: a-k)	nFORM, OLLE
Healthy Partner Behavior	1 item: feelings of being overwhelmed as parent (categories, 4 point scale)	nFORM Community-Based Fathers Survey (B3 – B3a)	nFORM

* you may add rows by hitting the tab button, or right click and select insert row below

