Gentle Warriors Academy Healthy Marriage and Responsible Fatherhood Program Evaluation

4/22/2024

Clinicaltrials.gov ID: NCT06899100

Statistical Analysis Plan

1. Data Analysis

Briefly describe the planned approach for data analysis. If an impact analysis is proposed, name the key dependent and independent variables, and describe any methods to minimize Type I error (i.e., finding positive impacts by chance) such as limiting the number of impacts to be analyzed and/or multiple comparison correction. Describe proposed approach(es) for addressing missing data.

Analytic Sample

The study sample includes participants who: 1) gave recorded informed consent to be part of the study, and 2) took both an entrance and exit survey. The analytic sample for particular outcome measure will vary based on missing data.

Outcome measures

For each outcome construct, we have identified the relevant measures from nFORM and the OLLE survey that are theoretically aligned with that construct. We will generate a correlation matrix between items in a given construct to ensure that theoretically related items are also empirically related in our data set. Items that are not strongly correlated with other items in a construct will be removed as necessary. Factor analysis will be used to ensure that all construct items hang together (using an alpha of 0.7 or higher as the threshold).

Once we are confident that all of the items align with a given construct, we will create a composite measure by taking an average of the scores on each non-missing item in the construct. The measure definition matrix below provides information on each proposed outcome. For composite measures, a change score will be calculated between a participant's pre-program composite score and post-program follow-up composite score. For standalone survey items, a change score will be calculated between a participant's pre-survey and follow-up survey responses.

For the sake of consistency and simplicity, parenting and co-parenting analyses will use a participant's youngest child as the focal child.

Construct	Sample	Measure	Data source(s)	Variable Name
Parenting Attitudes (toward children)	Has at least one child age 24 or younger	7 items: frequency of key attitudes (categories, 5-point scale)	nFORM entrance, OLLE follow-up	Copar_Att

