Parenting Behaviors (interaction with children)	Has at least one child age 24 or younger, saw child within past month	Continuous (1 item: hours spent w/children in last 30 days (interval); 1 item: frequency reach out to children (categories, 5-point scale); 7 items: frequency engage in key behaviors (categories, 5-point scale)	nFORM entrance, OLLE follow-up	Par_Beh
Co-parenting behavior	Has at least one child age 24 or younger, saw child within past month	11 items: frequency of agreement with key co-parenting behaviors (interval, 5-point scale)	nFORM entrance, OLLE follow-up	CoPar_Beh
Healthy Partner Behavior(Well-being as a parent)	Has at least one child age 24 or younger	1 item: feelings of being overwhelmed as parent (categories, 4 point scale)	nFORM entrance and exit	Well_being

Data preparation

We plan to clean each individual raw data file before merging nFORM and local evaluation surveys together for analysis in R using nFORM Client ID as the linking variable. Quality checks will include checks for duplicate surveys, incorrectly entered nFORM IDs, missing data, and outliers. We will look at descriptive statistics for our variables of interest to look for missing and outlying data.

Approaches to address missing data

Outcomes

When creating the composite measures for co-parenting and parenting relationships, we will create a composite score by taking the average of multiple individual items. For these measures, our current plan is to use 20% as a threshold for allowable missing items, based on guidance from evaluation technical assistance resources. This plan is contingent on the final distribution of missing data in our data set. With a 20% threshold, if a respondent is missing more than 1 item used for creating the co-parenting construct or more than 2 items for creating the parenting construct, the respondent will be assigned a missing value for that construct. We will not be imputing truly missing values for outcomes. To create a construct score, the average will divide by the number of non-missing values in the construct.

Participants who have not seen their child within the past month will have their parenting behavior responses set to “Never” (1) and will be included in the analytic sample for that outcome.

For outcomes that use single survey items, participants who do not respond to the item on either the pre- or follow-up survey will be excluded from the analytic sample for that outcome.

Assessing non-response bias

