We will conduct response rate analysis for each primary outcome of interest to assess non-response bias and adjust for threats to internal validity. Using data from the Applicant Characteristics Survey, we will look at demographics (race, ethnicity, age, education level) and primary reason for joining the program among participants who fall into each of the following categories: 1) non-respondents who answered no surveys after the ACS, 2) respondents who completed the pre-survey only, 3) respondents who completed the post-survey only, and 4) respondents who completed both the pre- and follow-up survey (complete case).

Subgroup Analyses

We plan to compare data across two sets of subgroups. These are participants (fathers) whose ages range from 18-29 and those over the age of 30. We also plan to compare data across incarcerated participants and community participants.

Analytic approach

The main goal of this descriptive study is to assess pre-post change scores in the outcomes listed above among program participants before and after primary workshops. The changes will be assessed from program enrollment to one year after the enrollment (follow-up survey). We will use paired sample t-tests to assess the magnitude and significance of changes among program participants in the analytic sample for each outcome. We will adjust our p-values for multiple hypothesis testing and report the adjusted p-values in the appendix of the final report.

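### The SAP states two conflicting samples for parenting behavior (confirmatory R1), and its Never recode is worded to cover items it does not fit

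*SAP*

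**What the plan says.** Protocol 1.1 lists R1, healthier parenting behavior, as a primary outcome. Protocol 1.2 marks it confirmatory, which that table defines as "Confirmatory: those upon which conclusions will be drawn". The target population in Protocol 1.2 and 7.1 is urban fathers aged 18 or over with children up to 24, with no condition on recent contact.

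In SAP section 1, the Sample column of the measure definition matrix gives this for parenting behavior (Par_Beh): "Has at least one child age 24 or younger, saw child within past month". Under the approaches to missing data for outcomes, the SAP says "Participants who have not seen their child within the past month will have their parenting behavior responses set to" the lowest category, Never (1). The same sentence goes on to say that these fathers "will be included in the analytic sample for that outcome". The general rule under Analytic Sample requires consent and both surveys, and adds: "The analytic sample for particular outcome measure will vary based on missing data".

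Protocol 8.1 builds the construct from nine items: hours with children in the last 30 days (interval), frequency of reaching out (5-point), and seven engagement items (5-point). The instrument is listed as "nFORM Community-Based Fathers Survey (A2b, A2c, A5b: b-d, f-i").

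The test for each outcome is stated under Analytic approach: "We will use paired sample t-tests to assess the magnitude and significance of changes among program participants in the analytic sample for each outcome". Change runs from enrollment to one year.

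**The concern.** The same fathers are outside the R1 sample under the matrix and inside it under the missing-data text. The two rules answer different questions. The matrix rule estimates change in behavior among fathers who are seeing their child. The inclusion rule estimates change among all fathers, and counts a regained or lost contact as a large rise or fall in parenting behavior. Two analysts could follow this SAP and report different results for a confirmatory outcome.

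The recode raises a second difficulty. It covers parenting behavior responses without naming items, and the construct mixes frequency scales with an hours item. Followed literally, it would write 1 into an hours field for a father who saw no child. It would also overwrite a valid outreach answer from a father who calls or writes but does not visit.

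**Working it through.** **No figure to reproduce.** The documents give no contact rate, mean, SD or sample size for this outcome. The check is a comparison of the texts, followed by an illustration on assumed inputs.

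**Which rule governs.**
- The inclusion sentence is specific to the outcome and names the fathers whom the matrix row leaves out.
- The general sample rule refers to missing data, and the inclusion sentence stands under missing data. This favors inclusion.
- Just before the recode, the SAP says it will not impute values that are truly missing. That suggests a contrast with answers absent because the child was not seen, and again favors inclusion.
- Against this, the column is headed Sample, and its other condition (a child aged 24 or younger) is an eligibility rule. The co-parenting row has the same contact condition with no inclusion sentence, so there the column is the only stated contact rule. Reading it as mere question routing in one row and as a sample restriction in the next needs an explanation that the SAP does not give.
- No text ranks the two rules or labels one a sensitivity analysis.

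**Which items the recode touches.** Taken in the order listed in Protocol 8.1, A2b is hours, A2c is outreach, and A5b b-d (3 items) plus f-i (4 items) are the 7 engagement items, so 1 + 1 + 7 = 9. The mapping of A2b and A2c is inferred from that order. Never (1) fits the seven engagement items. It is not a category of an interval hours item, and it need not be the true outreach answer of a father without visits.

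**Illustration, engagement items only; every input is assumed.** The mean is 3.5 when the child is seen and 1 when not, so d = 2.5. A share u = 0.25 have no contact at baseline; of these, g regain contact. Of the others, l lose it. Fathers in contact at both waves change by s; those who regain contact score 3.5 at follow-up.

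- Both waves = (1-u)(1-l); lost = (1-u)l; regained = u·g; neither = u(1-g)
- Contact required at both waves: mean change = s
- All fathers included: mean change = s·both + d·(regained - lost)

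| Scenario | g | l | Both | Lost | Regained | Neither |
|---|---|---|---|---|---|---|
| A | 0.40 | 0.10 | 0.6750 | 0.0750 | 0.1000 | 0.1500 |
| B | 0.60 | 0.10 | 0.6750 | 0.0750 | 0.1500 | 0.1000 |
| C | 0.20 | 0.15 | 0.6375 | 0.1125 | 0.0500 | 0.2000 |

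With s = 0, the restricted rule gives 0. The all-fathers rule gives:
- A: 2.5 × 0.025 = +0.0625
- B: 2.5 × 0.075 = +0.1875
- C: 2.5 × (-0.0625) = -0.1563

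With s = 0.20, the restricted rule gives +0.20. The all-fathers rule gives:
- A: 0.1350 + 0.0625 = +0.1975
- B: 0.1350 + 0.1875 = +0.3225
- C: 0.1275 - 0.1563 = -0.0288

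With s = 0.20 the signs differ once lost minus regained exceeds s·both/d: 0.20 × 0.675/2.5 = 0.054 (A, B) or 0.20 × 0.6375/2.5 = 0.051 (C). Net loss is -0.025, -0.075 and +0.0625, so only C crosses the line. Requiring contact at both waves drops 1 - both: 32.5% (A, B) or 36.25% (C) of fathers.

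**Effect on the test, a second assumed set.** Take 300 fathers, an in-contact score of mean 3.8 and SD 0.6, and a change among those in contact at both waves of mean 0.20 and SD 0.6. Let 80% be in contact at both waves, 10% lose contact, 5% gain it and 5% have none.
- Restricted: n = 240, t = 0.20/(0.6/√240) = 5.16
- All fathers: mean = 0.8 × 0.20 + 2.8 × (0.05 - 0.10) = 0.02; variance = 0.8(0.36 + 0.04) + 0.15(0.36 + 7.84) - 0.0004 = 1.5496; SD = 1.245; t = 0.02/(1.245/√300) = 0.28

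If instead 5% lose contact and 10% gain it, the all-fathers mean is 0.30 and t = 4.30.

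**The case against.** The best defense is that the SAP has in effect decided. It says in advance that fathers without contact "will be included in the analytic sample for that outcome", and that sentence has no purpose except as an exception to the matrix row. On this view the cell is a leftover phrase. Much of this stands: inclusion is the likelier intent. A reader might infer that the SAP leaves the sample wholly open, to be picked once results are known; the documents do not support that. They do contain an unresolved contradiction on a confirmatory outcome, and likely intent is not a stated rule.

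A reader might also infer that the wave at which contact is judged is undecidable. That goes too far. Composites are scored separately at entrance and follow-up and then differenced, and the past month is naturally counted back from each survey. One clarifying sentence is enough.

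It can fairly be said that Never (1) was meant only for frequency scales, and that the skip pattern depends on questionnaires not supplied. So it cannot be claimed that hours or outreach answers will in fact be corrupted. What stands is that the wording does not exclude it.

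Finally, every illustrative input is assumed, the sign changes in only one of the three scenarios, and a gap of 2.5 points belongs to the engagement items, not the nine-item composite. All of this is correct and limits what the numbers can show.

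**Conclusion.** The point holds. The Sample cell and the inclusion sentence for Par_Beh cannot both be followed, they estimate different quantities for R1, and no text says which prevails. The recode, as worded, also extends to items for which Never (1) is not a valid or necessarily true answer. Both should be settled before R1 is analyzed.

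The size is unknown. The illustration shows only that the two rules can practically agree (A, with a gain of 0.20) or differ in sign (C), depending on how many fathers gain or lose contact. A reader might take it as evidence that this study's R1 result would be reversed; it is not. It rests on assumed contact rates and scores, covers the engagement items rather than the full composite, and models the matrix rule only as contact at both waves.

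**What to change.** 1. Delete the past-month contact phrase from the Par_Beh row, so that the matrix agrees with the inclusion sentence and the protocol population. If change among fathers in contact is the intended primary quantity, say so and delete the inclusion sentence instead.
2. State that contact is judged separately at entrance and at the one-year follow-up.
3. Limit the Never (1) recode to the seven engagement items (A5b: b-d, f-i). Keep any reported outreach and hours answers. Code hours as 0 only where the questionnaire skipped the item because the child was not seen, after checking the skip pattern.
4. Report R1 among fathers in contact at both waves as a sensitivity analysis, with the number of fathers in each of the four contact patterns (seen or not seen, at entrance and at follow-up). It suits a sensitivity analysis because contact at follow-up is something the program may itself affect.

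The cost is a few lines of SAP text, a small recode and one table, provided contact is asked at both waves. The downside is that the all-fathers result mixes change in contact with change in behavior; item 4 lets the reader see how much of it is contact.

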2. EVALUATION GOALS

Please briefly describe key goals of your evaluation and what you hope to learn below.

In this evaluation, it is anticipated that participants will show an increase in:

- Communications and handling conflict and other related relationship skills
- Understanding in role as a father
- Improved communication with partner/co-partner
- Understanding the quality of father-child engagement
- Various forms of contact with children

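### The SAP's 'Never' recode for fathers who have not seen their child exempts no Parenting Behavior item, so as written it also covers reaching out and hours, and it conflicts with the measure matrix

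*SAP*

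**What the plan says.** In SAP section 1, under the approaches to missing data for outcomes, the rule reads: "Participants who have not seen their child within the past month will have their parenting behavior responses set to" *Never* (1). It adds that these fathers "will be included in the analytic sample for that outcome".

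The measure matrix in the same section defines the Parenting Behaviors sample differently: "Has at least one child age 24 or younger, saw child within past month".

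The matrix lists three kinds of item in that construct:

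- hours: "1 item: hours spent w/children in last 30 days (interval";
- reaching out: "1 item: frequency reach out to children (categories, 5-point scale";
- engagement: "7 items: frequency engage in key behaviors (categories, 5-point scale".

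Protocol section 8.1 gives the same content and labels the items A2b, A2c and seven parts of A5b. Taken in the order listed, these are hours, reaching out and engagement. The composite is the mean of the non-missing items, and the change score runs from enrollment to the one-year follow-up. R1 is marked primary in Protocol section 1.1 and confirmatory in section 1.2. Protocol section 2 lists "Various forms of contact with children" among the expected gains.

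**The concern.** Scoring *Never* is defensible for engagement items that need the child to be present. It does not suit the other two kinds of item.

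- **Reaching out (A2c).** A father can call or write without seeing his child. If he answered this item, the rule replaces his answer with the scale minimum.
- **Hours (A2b).** This is a count on an interval scale. A literal recode credits one hour to a father who had none.

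At stake is the score for a confirmatory outcome. Improved outreach by a father who still does not see his child would not register. Unchanged outreach by a father who regains contact would register as improvement. The matrix adds a second problem, because two analysts following different parts of the same section would analyse different samples.

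**Working it through.** The plan gives no figure to reproduce here. It states no share of fathers without contact, no reach-out distribution and no SD, so the values of p, m and the individual scores below are assumptions.

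**Inputs from the documents.** There are 1 + 1 + 7 = 9 items, of which eight are on a 5-point scale. The composite is the item mean and the recode value is 1. Hours are set aside at first because no scaling is given.

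**1. Unseen at both waves.** Under the rule all eight items equal 1 at both waves, so recorded change is 0. With reach-out kept as answered and the seven engagement items at 1, change = (r1 − r0)/8.

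- Reach-out 2 to 4: 2/8 = +0.25, recorded as 0.
- Reach-out 1 to 5, the extreme: 4/8 = +0.50, recorded as 0.

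**2. Unseen, then seen.** Assume that at follow-up the engagement items are 3 and reach-out is 4, with baseline reach-out also 4.

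- Follow-up composite: (7×3 + 4)/8 = 3.125.
- Baseline under the rule: 8/8 = 1, so change = +2.125.
- Baseline with reach-out kept: (7×1 + 4)/8 = 1.375, so change = +1.75.
- Overstatement: 2.125 − 1.75 = 0.375 = (4 − 1)/8. The maximum is (5 − 1)/8 = 0.50.

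**3. Seen, then unseen.** The mirror case gives −2.125 instead of −1.75, so the loss is overstated by 0.375.

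**4. Group mean.** Let p0 and p1 be the unseen shares at the two waves, and m0 and m1 the mean reach-out scores of those fathers. Error in mean change = [p0(m0 − 1) − p1(m1 − 1)]/8.

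| p0 | p1 | m0 | m1 | Error |
|---|---|---|---|---|
| 20% | 20% | 2 | 4 | (0.2 − 0.6)/8 = −0.05 |
| 40% | 40% | 2 | 4 | (0.4 − 1.2)/8 = −0.10 |
| 80% | 80% | 2 | 4 | (0.8 − 2.4)/8 = −0.20 |
| 40% | 20% | 3 | 3 | (0.8 − 0.4)/8 = +0.05 |
| 40% | 20% | 4 | 4 | (1.2 − 0.6)/8 = +0.075 |
| 20% | 30% | 3 | 3 | (0.4 − 0.6)/8 = −0.025 |
| 20% | 20% | 3 | 3 | 0 |

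**5. Hours.** If raw hours entered a nine-item mean, writing 1 for 0 would shift that wave's score by 1/9 = 0.11. This cancels in the change score for a father unseen at both waves.

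**6. If reach-out is not asked of these fathers.** The mean of seven items at 1 is 7/7 = 1, and the mean of eight items at 1 is 8/8 = 1. The score on the 5-point items is then the same with or without the recode of A2c, so the loss in steps 1 to 4 depends on the item being answered.

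**The case against.** **The rule may only fill blanks.** It sits under the missing-data heading, just after a statement that truly missing outcomes are not imputed. It may be meant for items left blank because the child was not seen. This is a fair reading, and without the survey it cannot be excluded. The SAP does not say so, however, and outreach would still be entered as *Never*.

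**Only the seven engagement items may be meant.** *Never* cannot sensibly apply to hours, which suggests a narrower intent. That is plausible, but no item is exempted and an analyst would have to guess.

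**The matrix may govern.** In that case these fathers are excluded and nothing is overwritten. Their outreach would still not count, and the matrix would still contradict the inclusion sentence.

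**Item screening may drop A2c.** The SAP removes weakly correlated items. It does not say whether screening comes before the recode. Setting all items to 1 together would raise their correlation and make removal less likely.

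**Stronger readings the documents do not support.** A reader might infer that R1 would measure access to the child rather than parenting, and that exempting A2c cures this. In step 2, 1.75/2.125 = 82% of the swing remains after the fix, because it comes from the engagement items. A reader might also infer that remote contact is erased altogether. A2c is untouched for fathers who saw the child, the content of the A5b items is not shown, and the protocol's goal refers to forms of contact without singling out remote contact.

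**Conclusion.** The point holds in a limited form. Followed literally, the rule puts the scale minimum on an item that does not depend on seeing the child and a category code on an hours item, in a confirmatory outcome. It also contradicts the sample definition in the matrix.

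For an individual father the error on the eight-item mean is at most 0.50 points, provided that A2c is answered when the child was not seen. It would be tempting to conclude that R1 is biased in a particular direction. The documents give no basis for that: the error can be negative, positive or nil, and it is probably modest because one item in eight carries it. The largest value in the table needs 80% of fathers unseen at both waves and a two-point rise in their outreach.

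This should be fixed before analysis. Confidence is medium, because the survey's routing and the authors' intent are not shown.

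**What to change.** Revise the SAP rule and the matrix row as follows:

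- Limit the *Never* recode to the seven A5b engagement items.
- Keep A2c as answered, and treat it as missing if it was not asked.
- Score A2b as 0 hours when the child was not seen. Either rescale it before averaging, with the scaling stated, or analyse it separately, since raw hours cannot be averaged with 1–5 items.
- Apply the same rule at enrollment and at one year. The matrix takes the two waves from different instruments (nFORM entrance, OLLE follow-up), so check in both whether A2c is asked of these fathers.
- Make the matrix sample definition agree with the inclusion sentence.

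The cost is a few lines of SAP text and a small change to the scoring code, with no new data.

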8.3. METHODS OF DATA COLLECTION

If the evaluation will collect multiple waves of data, describe the timing of these waves below. When describing follow-up periods, specify whether the follow-up period will be post-baseline, post-random assignment, or post-program completion.

Wave of Data Collection (e.g., baseline, short-term follow-up, long-term follow-up)	Timing of Data Collection
Baseline	Collected Immediately Following informed consent and enrollment – during and orientation session or first workshop.
Post-Test	Collected after the completion of core curriculum programing -during the last workshop session – approximately 13 weeks after enrollment.
1 year Follow-up (post-baseline)	Collected approximately one year after program enrollment/ baseline

For each measure, describe how data will be collected detailing which data collection measures will be collected by which persons, and at what point in the programming or at what follow-up point.

Measure	Timing of Data Collection (baseline, wave of data collection)	Method of Data Collection	Who Is Responsible for Data Collection?	Administrative Data Only: Will data access require data sharing agreement?
On Line Local Evaluation (OLLE) Baseline Survey	Baseline	Participant Self-Entered survey using online data collection program	Data Manager will proctor data collection and assist participants as necessary	No
OLLE Post-Test Survey	Post-Test (approx. 13 weeks after enrollment)	Participant Self-Entered survey using online data collection program	Data Manager will proctor data collection and assist participants as necessary	No
OLLE 1 Year Follow-up Survey	1 year after enrollment / baseline	Participant Self-Entered survey using online data collection program and link – or – Phone Interview data collection	MER Research Staff/ participant tracking team	No

* you may add rows by hitting the tab button, or right click and select insert row below

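### The SAP's four non-response groups do not single out fathers with entrance and exit surveys but no one-year survey, so for R1–R3 the check cannot show whether loss at the endpoint is selective

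*SAP*

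**What the plan says.** Protocol 8.3 sets three waves: baseline, a post-test in the last workshop session at about 13 weeks, and a follow-up "Collected approximately one year after program enrollment/ baseline". Protocol 8.4 treats the post-program and one-year surveys as separate collections with different methods. Protocol 1.2 places all four confirmatory outcomes "one year after GWA Project enrollment".

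The SAP (Analytic Sample) admits consenting fathers who "took both an entrance and exit survey". Under Analytic approach it states: "The changes will be assessed from program enrollment to one year after the enrollment (follow-up survey". Its measure table takes parenting attitudes, parenting behavior and co-parenting behavior (R2, R1 and R3) from the nFORM entrance survey and the OLLE follow-up. The Well_being item, which stands for R4, comes from nFORM entrance and exit.

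Under Assessing non-response bias, the SAP plans a response analysis for each primary outcome, using demographics and reason for joining from the Applicant Characteristics Survey (ACS). The groups are "non-respondents who answered no surveys after the ACS", then "respondents who completed the pre-survey only, 3) respondents who completed the post-survey only", and finally "respondents who completed both the pre- and follow-up survey (complete case". Missing outcomes are not imputed, and neither document plans another non-response comparison.

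**The concern.** A father with entrance and exit surveys but no one-year survey has more than a pre-survey, more than a post-survey, and is not a complete case. Yet the SAP counts him in the study sample, and for R1–R3 he has no endpoint.

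Loss before week 13 and loss after it come about differently. Under Protocol 8.3 and 8.4, the exit survey is proctored in the last session, so it depends on program retention. The one-year survey is by link or phone, through a tracking team, and depends on finding the father again roughly nine months later (52 − 13 = 39 weeks). The modest attrition expected in Protocol 8.4 rests on retention in the program; no expectation is given for one year.

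This is an uncontrolled pre-post study without outcome imputation, so selective loss at one year passes straight into the reported change. A check that does not isolate the fathers lost at that stage could look reassuring without bearing on the loss that matters.

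**Working it through.** The plan gives no figure to reproduce, so the check is an enumeration.

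**Inputs.** Three waves (Protocol 8.3, 8.4); study sample = entrance and exit (SAP, Analytic Sample); four groups (SAP, Assessing non-response bias), numbered 1 to 4 in the SAP's order. Three yes/no surveys give 2 × 2 × 2 = 8 patterns.

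**Readings.** The SAP does not define post-survey, so three readings were tried:
- A: post-survey is the exit survey, and 'only' means no other survey.
- B: post-survey is the one-year survey, and 'only' means no other survey.
- C: post-survey is the one-year survey, and the exit survey is disregarded.

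| Entrance | Exit | One-year | A | B | C | Study sample |
|---|---|---|---|---|---|---|
| no | no | no | 1 | 1 | 1 | no |
| no | no | yes | none | 3 | 3 | no |
| no | yes | no | 3 | none | none | no |
| no | yes | yes | none | none | 3 | no |
| yes | no | no | 2 | 2 | 2 | no |
| yes | no | yes | 4 | 4 | 4 | no |
| **yes** | **yes** | **no** | **none** | **none** | **2** | **yes** |
| yes | yes | yes | 4 | 4 | 4 | yes |

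**Results.**
1. Readings A and B each place 5 of 8 patterns, and entrance plus exit without one-year is unplaced under both. Reading C places 7 of 8 and puts that pattern in group 2, together with fathers who took only the entrance survey.
2. Only the last two rows belong to the study sample. Under A and B, groups 1 to 3 lie wholly outside it. Under C, group 2 mixes study-sample fathers with others.
3. On none of the three readings is the second-to-last row set against the last row, which is the comparison that bears on loss between exit and one year.
4. Group 4 also admits fathers with entrance and one-year surveys but no exit survey. They are outside the study sample, so group 4 as worded is not the analysed set either.

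**Size.** Let *r* be the share of the study sample answering at one year, *d*R the mean change in those who answer and *d*N the mean change in those who do not. The full-sample change is *r·d*R + (1 − *r*)·*d*N, so the complete-case result is off by (1 − *r*)(*d*R − *d*N). Neither document gives *r*. Purely as an assumption, *r* = 0.80 gives 1 − 0.80 = 0.20 and *r* = 0.60 gives 1 − 0.60 = 0.40. The error would then be 20% to 40% of the difference between the two sets of fathers. That difference is unknown too.

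**The case against.** The strongest reply is that the four groups form a two-by-two of one survey pair: neither, first only, second only, both. Group 4 names the pair as pre and follow-up. The SAP also uses 'post' for the one-year measure elsewhere: it describes the later composite score as post-program and follow-up at once, and it calls the change to one year a pre-post change. Because the analysis is run per primary outcome, the pair may simply follow each outcome's data sources. On that reading (C), the fathers in question are in the pre-survey-only group and are compared with complete cases.

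This stands as far as it goes. A reader might infer from the literal wording that these fathers are certainly left out and never compared; the documents do not support that, because reading C is reasonable. What survives is the pooling. Fathers who finished the program and were lost at one year would be merged with fathers who never reached exit, so a difference confined to the first set could be diluted or masked.

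It can also be said that 'exit' in the sample definition may itself have been meant as the endpoint survey, in which case no study-sample father would lack it. The documents treat exit and one-year as distinct, so this cannot be assumed; and even then, fathers lost after exit would not be shown separately.

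Nor should the check be described as comparing complete cases with early dropouts alone: if post-survey is the week-13 survey, group 3 attended the last session.

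**Conclusion.** The point holds in this form: the four groups do not separately identify fathers with entrance and exit surveys but no one-year survey. They are unplaced on a strict reading and pooled with pre-exit losses on the looser one. For R1–R3 they are the study-sample fathers lost to the one-year endpoint through survey non-response, so the planned check cannot show whether that loss is selective.

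This rests on the exit and one-year surveys being separate waves and on the sample definition meaning what it says. It concerns missing surveys; unanswered items within a returned survey are a separate route to loss. It does not carry over directly to Well_being: on the measure table's entrance/exit source these fathers would be analysed, although they still have no row of their own.

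A reader might infer that a known share of the sample is affected, or that the one-year change is biased. Neither follows. The 20% to 40% above is only the complement of an assumed response rate, and nothing in the documents shows that the loss is selective. The paired t-tests are unaffected; the defect is in the bias check meant to support them, and it should be corrected.

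**What to change.** 1. Define the entrance (pre), exit (post) and one-year follow-up surveys in the SAP and use those terms throughout.
2. Replace the four groups with groups defined by all three waves, so that all eight patterns have a place.
3. For R1–R3, make the key comparison entrance plus exit without one-year against entrance plus exit with one-year, both within the SAP study sample. Show entrance plus one-year without exit as a separate row, so that it does not blur that comparison.
4. Add baseline outcome scores to the ACS characteristics. Add the 13-week change only where the exit survey is confirmed to carry the same items; the SAP's measure table does not list exit data for R1–R3.
5. For Well_being, use the entrance/exit pair if that data source is kept.

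The cost is SAP wording and a slightly longer table. The surveys are already part of the plan, so no new data collection is needed.
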